11.2 PRODUCT COMPLAINT/DEVICE DEFICIENCY DEFINITION

A product complaint/device deficiency is defined (21 CFR 820.3(b) and ISO 14155) as any alleged deficiency related to the identity, quality, durability, reliability, safety, effectiveness, or performance of a device. This may include malfunctions, use error and inadequacies in labeling. Product complaints can pertain to any marketed JJSV device being used in the study as well as the investigational device. The investigator is to assess whether the deficiency could have led to a serious adverse event without suitable action or intervention or under less fortunate circumstances.

11.3 ADVERSE EVENT AND COMPLAINT REPORTING REQUIREMENTS

All adverse events and any complaint encountered using any JJSV product, regardless of severity and whether or not attributed to the study device(s), are to be reported to JJSV and recorded on the case report form corresponding to the visit during which awareness of the event occurred. Adverse events are also to be reported to the reviewing IRB as per the IRB reporting requirements. If required, adverse events will be reported to the appropriate regulatory agencies (e.g., FDA) according to all applicable laws and regulations.

Reporting of adverse events shall follow the USA Code of Federal Regulations (21CFR812).

General guidelines are provided below:

Adverse Event Reporting

An adverse event that is not serious or device-related is to be reported to JJSV in a timely manner. Notification of non-serious and non-device related adverse events will occur by recording events on the CRF when noted. Such adverse events are also to be reported to the reviewing IRB per their reporting requirements.

Complaints/Device Deficiency Reporting

A general product complaint or device deficiency is to be reported to JJSV in a timely manner. Notification of complaints/device deficiencies will occur by either recording complaints on the CRF when the complaint occurred (e.g. operative form) or by a phone call to the Sponsor. Any device deficiency that could have led to a serious adverse event without suitable action or intervention, or under less fortunate circumstances, must be reported to the sponsor immediately (no later than 24 hours after detection). Device deficiencies that could have led to a serious adverse event should also be reported to the investigator's IRB per their reporting requirements.

Serious and/or Device-Related Adverse Event Reporting

Serious and/or device related events (ADEs) are to be documented using the Detailed Adverse Event CRF. In the event of a serious adverse event (SAE), which may or may not be related to use of the study device, JJSV must be notified immediately (no later than 48 hours after detection). Any SAE is to be reported by phone (and/or email) and by submitting the completed Detailed Adverse Event CRF. Any SAE or device-related AE should also be reported to the investigator's IRB/IEC per their reporting requirements.

Unanticipated Adverse Device Effect (UADE)/Unanticipated Serious Adverse Device Effect (USADE) Reporting

If during the study, a serious adverse event occurs that may reasonably be regarded as device-related and was not previously expected in nature, severity, or degree of incidence, the investigator is to report the UADE/USADE to JJSV immediately (no later than 48 hours after detection), and to the investigator's IRB as soon as possible (and no later than 10 working days after learning of the event for sites in the USA as required by 21CFR812).

11.4 CAUSAL RELATIONSHIP

The investigator should always be alert to adverse events that may be related to the study device or the use of the study device (i.e., the procedure specific to the initial application of the device). An attempt should be made in every case to determine the causality of the event. The following definitions are to be used as guidelines in determining the relationship between the event and the study device and/or use of the device.

Definitely related:	If the event is associated with the device and/or the use of the device beyond a reasonable doubt, a causal relationship exists between the adverse event and the device and/or the use of the study device.
Probably related:	There is a reasonable possibility of a causal relationship between the adverse event and the device and/or the use of the study

device and/or the adverse event cannot be reasonably explained by another cause.

Possibly related: The adverse event has not been determined to be related to the device or the use of the device, but no other cause has been identified and the device and/or the use of the study device cannot be ruled out as a possible cause.

Unlikely to be related: The possibility of a potential causal relationship between adverse event and the device and/or the use of the device could exist, but the adverse event can be reasonably explained by another cause.

Not related: There is no possibility of a causal relationship between the adverse event and the device and/or the use of the study device and/or the adverse event can be attributed to another cause.

If an adverse event is believed to be definitely, probably or possibly related to the study device and/or the use of the device, the event will be considered related to the study device and/or the use of the device.

11.5 ADVERSE EVENT FOLLOW-UP

For every adverse event, appropriate measures should be undertaken to treat and/or monitor the subject until resolution occurs. Obtain and maintain in the subject's files all pertinent medical data relating to the event including the subject's medical records and medical reports and/or judgments from colleagues or outside specialists who assisted in the treatment and follow-up of the subject. The investigator should keep JJSV closely informed as to the outcome of serious and/or device-related adverse events, thereby allowing JJSV to comply with the appropriate regulatory reporting requirements. A Detailed Adverse Event Update CRF should be completed each time the subject returns to the investigator or other specialist(s) for follow-up of serious and/or device-related adverse event until resolution of the event. Any subject who is exited from the study due to a serious and/or device-related adverse event will be followed until the outcome is determined.

12. PROTOCOL CHANGES/AMENDMENTS

If the investigator desires to modify any procedure and/or the design of the study, he or she must contact and obtain consent from JJSV regarding the proposed changes prior to implementation. Any modifications (including additional data collection) require approval by the FDA and all other appropriate regulatory agencies, as well as approval of the governing IRB prior to implementation.

13. ETHICS REVIEW AND PATIENT WELFARE

13.1 INSTITUTIONAL REVIEW BOARD (IRB)

It is the responsibility of the investigator to obtain prospective approval of the study protocol, protocol amendments or changes, informed consent forms and other relevant documents (e.g., advertisements) from the IRB. All correspondence with the IRB should be retained in the Investigator Notebook. Copies of IRB submissions and approvals should be forwarded to JJSV.

The investigator is responsible for notifying the IRB of reportable adverse events as well as any other circumstance in which additional procedures outside the protocol were conducted to eliminate apparent hazards to subjects.

13.2 INFORMED CONSENT

The informed consent document will be provided as a physical or electronic document to each study subject for review prior to consenting. If using the electronic document, the study subject will be given an electronic tablet with the preloaded IRB-approved study specific informed consent. The current version of the IRB-approved study informed consent must be signed by each study subject prior to any study-specific examinations being performed. The IRB approved informed consent is to be signed and dated by the subject as well as by the person who conducted the informed consent discussion. Consent will be documented with required signatures on the physical document or on the electronic document. The signed informed consent will be maintained by the investigator as a permanent part of the subject's medical records. A copy of the signed and dated form is to be provided to the subject. If the electronic document is used for consenting, study subjects can elect to receive either a printed or electronic copy of the informed consent documents. Signed and submitted informed consent documents will be available as PDFs in the electronic consent repository. The investigator will provide JJSV written acknowledgement on the preoperative case report form that a signed agreement of informed consent has been obtained and is in the investigator's possession for each subject. As required by 21CFR812 Part G, the site shall document in the source documents that informed consent was obtained prior to participation in the study for each subject enrolled.

NOTE: The informed consent process also includes obtaining the subject's signature on an Authorization for Use/Disclosure of Health Information for Research Form or equivalent documentation necessary to comply with applicable privacy laws pertaining to medical treatment in the governing countries.

NOTE: The sponsor will secure appropriate insurance for study subjects prior to study start.

14. DOCUMENTATION

14.1 SOURCE DOCUMENTS

Source documents must be kept for all study subjects. Source documents may include a subject's medical records, hospital charts, clinic charts, the investigator's subject study files, as well as results of any diagnostic tests or procedures such as topographies or laboratory tests with photographs or instrument printouts.

Each site is expected to adhere to the clinic's own standard documentation requirements for medical charts/clinic notes. However, for the purposes of this clinical study, the medical charts/clinic notes must also include, at a minimum, the following data that will be considered source data and will be reviewed by JJSV:

- Subject's name and study identification number
- Subject's contact information
- Study protocol number and the Sponsor name (JJSV)
- A statement that informed consent was obtained prior to participation in the study (including the date)
- Evidence of subject eligibility
- Dates of all subject visits and surgeries throughout the duration of the study
- OVD serial number identification (NOTE: This is masked information, and may only be reviewed by unmasked study staff)
- Concurrent medications
- Corrected and uncorrected distance visual acuity
- IOP
- ECC
- Manifest refraction
- Occurrence and status of any operative complications, postoperative medical or lens findings and adverse events
- The date the subject exited the study, and a notation as to whether the subject completed the study or reason for early exit.

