10.4 RANDOMIZATION AND MASKING

A randomization list stratified by investigational sites will be created [REDACTED] [REDACTED] Subjects will be randomly assigned to receive either the Healon EndoCoat PRO or the Healon EndoCoat control in the first operative eye in a 1:1 ratio; subjects will then receive the OVD not used in the first-eye surgery in the fellow eye. Unmasked study personnel at the site will be trained in the randomization process through the EDC system and will randomize subjects as they are enrolled. Randomization will take place after the subject has signed the informed consent document, has met all inclusion and exclusion criteria, and the investigator has documented which eye will be the first to undergo surgery.

As part of the informed consent process, the investigator or delegate will explain to the subject the requirements of a randomized study and the differences between the two OVDs: the Healon EndoCoat PRO investigational OVD and the Healon EndoCoat control OVD.

The subjects, investigators, and the study technicians performing the postoperative exams are to be masked through study completion. [REDACTED]

Unmasked Clinical Research Associates (CRAs) will visit the site to confirm OVD traceability and to monitor Operative visit forms and source documents. All other JJSV study personnel will remain masked through the final study visits.

[figure not shown]

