15.2 ADMINISTRATIVE MONITORING

Administrative monitoring procedures will ensure that study devices, subjects, and forms can be traced and will allow monitoring of investigator progress and compliance.

Accountability and traceability of study devices will be monitored by trained JJSV personnel.

Study Device Accountability

Complete OVD accountability will be maintained at the investigative site by maintaining records of all investigational OVDs received from and returned to JJSV. A site log will be used to track OVDs for date of receipt, use and disposition/return to JJSV. This site log and any other OVD information will be maintained in the operative room study binder and monitored by JJSV personnel. During periodic site monitoring visits, JJSV personnel will review inventory records and logs to ensure OVD accountability compliance and complete OVD traceability.

Site Monitoring Plan

Prior to performing any study surgeries, the requirements of the study and reporting mechanisms will be explained to each investigator either personally at the investigative site or at a formal study investigator meeting. When necessary, a pre-study site qualification visit may be performed to assess the adequacy of the site to perform the study for sites that have not previously worked with JJSV or have undergone significant changes, or have not been visited in the past year. A study initiation visit will be conducted for all sites prior to or at the time of the first study surgery.

Throughout the duration of the study, site visits to monitor compliance to this protocol will be made at each investigative site. During a routine site monitoring visit, JJSV will review informed consent documents and subject eligibility, and the data on study case report forms will be verified against subject charts and other source documents to ensure complete and accurate reporting. The subject files will also be reviewed to assure that all adverse events and any issues encountered with JJSV products have been reported in a timely fashion.

JJSV will also review source documents to verify that all required items have been documented in the subject medical charts. Refer to Section 14.1, Source Documents, for a list of items that are required for source documentation. Additionally, study logs will be checked to ensure compliance with study procedures.

Training on study-specific procedures may also be conducted during monitoring visits.

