### 1.4 RANDOMIZATION AND MASKING

A randomization list stratified by investigational sites was created by a JJSV biostatistician who is independent and not involved in the study activities. Subjects are randomly assigned to receive either the Healon EndoCoat PRO or the Healon EndoCoat control in the first operative eye in a 1:1 ratio; subjects then receive the OVD not used in the first-eye surgery in the fellow eye. Randomization will take place after the subject has signed the informed consent document, has met all inclusion and exclusion criteria, and the investigator has documented which eye will be the first to undergo surgery.

The subjects, investigators, and the study technicians performing the postoperative exams are to be masked through study completion. To maintain subject/technician-masking through the 3-month study exams, a masking plan will be tailored for each site to detail how OVD assignment information will be concealed from masked technicians. Recommended steps to maintain masking include ensuring that all items pertaining to OVD assignment and records are kept separately from all other study documents and subject medical records until after completion of the final study visit. For example, OVD logs (indicating the OVD model used in each eye) may be kept in the operating room study notebook until completion of the final study visit, at which time they may be placed in the subject medical charts.

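### Does listing the OVD serial number as a required chart item in Protocol 14.1 open a route to unmasking?

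*Protocol*

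**What the plan says.** Protocol 14.1 introduces its list by saying that "the medical charts/clinic notes must also include, at a minimum, the following data that will be considered source data". One entry is "OVD serial number identification (NOTE: This is masked information, and may only be reviewed by unmasked study staff". The same list holds IOP and ECC, the measurements behind the two primary endpoints. It gives no time of entry for any item.

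Protocol 15.2, under device accountability, says that the site log and "any other OVD information will be maintained in the operative room study binder". Later in 15.2, the sponsor checks that the required items are in the subject charts and refers back to the 14.1 list.

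Protocol 10.4 sets the scope of masking: "The subjects, investigators, and the study technicians performing the postoperative exams are to be masked through study completion". It also states that "subjects will then receive the OVD not used in the first-eye surgery in the fellow eye". Unmasked site staff run the randomization, unmasked clinical research associates confirm OVD traceability and monitor the operative forms and source documents, and all other sponsor study personnel stay masked. Some text directly after the masking sentence is blacked out.

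SAP 1.4 repeats the masking sentence and adds that "a masking plan will be tailored for each site to detail how OVD assignment information will be concealed from masked technicians". It continues: "Recommended steps to maintain masking include ensuring that all items pertaining to OVD assignment and records are kept separately" from other study documents and from medical records until the final visit is complete. As an example, OVD logs "may be kept in the operating room study notebook until completion of the final study visit", after which they may go into the chart.

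**The concern.** Taken by itself, 14.1 makes a treatment identifier a compulsory part of the record that also holds the masked outcome data. Its only safeguard is a rule on who may read the entry. A coordinator working from 14.1, and expecting the chart check in 15.2, might enter the number at surgery in an ordinary operative note that the postoperative examiner later opens.

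Two features of the trial make that worth checking:

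- **The paired-eye design.** Learning the product used in one eye also tells the reader what was planned for the other.
- **A stated direction of risk.** Protocol section 16 says the effect on IOP may be higher with the investigational OVD because it is more viscous. An unmasked examiner would therefore have a directional expectation on the primary safety endpoint. Investigators also decide on unscheduled visits and which tests to do there (10.10), and they judge causality of adverse events (11.4).

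The instructions also differ in force. The chart requirement in 14.1 is mandatory, whereas the separation step in SAP 1.4 is a recommendation illustrated by a permissive example.

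**Working it through.** No arithmetic applies: the point depends on no rate, standard deviation, margin, power or sample size. The check is whether the passages can all be followed at once without exposing the assignment.

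| Question | Where answered | Answer |
|---|---|---|
| Must the number be a source record? | Protocol 14.1 | Yes, among the required chart items |
| Who may see it? | Protocol 14.1, note in the same item | Unmasked study staff only |
| Where is OVD information kept? | Protocol 15.2 | Operating room study binder |
| Until when is it kept apart? | SAP 1.4 (recommended step) | Until after the final study visit |
| When may logs enter the chart? | SAP 1.4 (example) | From the final study visit onward |
| Who checks it during the study? | Protocol 10.4 | Unmasked clinical research associates |
| Who settles local detail? | SAP 1.4 | A masking plan for each site |

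1. **Is there a contradiction?** There would be one only if 14.1 required entry in the chart before the final visit. It states no time for any item. The list also includes the date the subject left the study and whether the subject completed it, which cannot be known until the end. So it describes the finished chart, not a chart that must be complete on the day of surgery. Filing the number after the last visit satisfies 14.1 and SAP 1.4 together.

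2. **Can a site put the number in an open chart early and still comply?** Hardly. The note in 14.1 forbids review by masked staff, and an entry in a chart that masked examiners use would defeat it. It would also sit badly with the binder in 15.2. A site would have to overlook the note, 15.2 and its own masking plan.

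3. **Does the chart check in 15.2 force early entry?** It names no date for this item. Site visits run through the study and end with a close-out visit at completion. Under 10.4, unmasked associates do the traceability and source checks during the study, and 15.2 has inventory records and logs reviewed at periodic visits. The number can be verified in the binder first and in the chart after the subject's last visit.

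4. **Are investigators protected as well as technicians?** The sentence on the site masking plan in SAP 1.4 names technicians only. The step that follows keeps assignment records out of the medical records altogether, and that protects against any reader of the chart, investigators included.

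5. **Would the number disclose the product?** The protocol treats it as masked information, so caution is right. No visible text says that the number alone identifies the product to someone without the log. The disclosure of both eyes is therefore conditional on that link.

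**The case for a change.** The best case for a change is that the one binding statement on the chart points toward inclusion, while the timing rule is only recommended and sits in the SAP, which site staff may never open. Section 15.2 points both ways, since it keeps OVD information in a binder and then has the 14.1 items verified in the charts without exempting this one. One sentence would remove the doubt, using a binder and unmasked monitors that already exist.

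Part of this stands. 14.1 carries no cross-reference, 15.2 gives no release time, and the chart check is not expressly limited to unmasked monitors. A sponsor revising the protocol for other reasons could reasonably align the three passages. If so, the 15.2 check would need the same wording as 14.1, or it would still send monitors to the chart for an item held elsewhere.

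It does not follow that the plan needs changing. Sites are to work from a masking plan written for them, so they need not find the rule in the SAP unaided. The blacked-out text in Protocol 10.4 follows the same sentence that, in SAP 1.4, leads straight into the masking-plan and separation wording. The protocol may already contain it, though this cannot be confirmed. Section 17 might be cited as giving investigators access to the charts, but it is a record-retention clause and says nothing about how an identifier is held during follow-up.

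**Conclusion.** No change is called for. Protocol 14.1 is correctly described as silent on timing and storage for the OVD serial number, but this is a gap in detail that sites and the sponsor would fill sensibly from the note in the item itself, 15.2, 10.4 and the site masking plan. Followed together, these passages preserve the masking of subjects, investigators and technicians through the final visit.

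The size is one list item without a cross-reference. No effect on the IOP spike comparison (10% margin), the ECC comparison (5% margin), type I error or power is shown, and none can be calculated from the documents.

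The conclusion assumes that the site masking plans are written as SAP 1.4 promises and follow its recommended separation, and that verification of this item before the final visit is left to the unmasked associates. It does not depend on what the redacted part of 10.4 says. If that text repeats the SAP wording, even the missing cross-reference largely disappears.
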